3.5.2. Laboratory Data

Safety laboratory tests will be performed as described in the protocol. To determine if there are any clinically significant laboratory abnormalities, the haematological, clinical chemistry (serum) and urinalysis safety tests will be assessed against the criteria specified in the sponsor reporting standards. The assessment will not take into account whether each participant's baseline test result is within or outside the laboratory reference range for the particular laboratory parameter.

For each period, the baseline measurement is the predose measurement on Day -1.

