- a. Screening will be performed within 28 days prior to the first dose of PF-07284890.
- b. Period 2 will begin on Study Period 1, Day 5 (referred to as Period 2, Day -1). Period 3 will begin on Study Period 2, Day 5 (referred to as Period 3, Day -1). Day -1 activities will be performed only for Day -1 of Period 1 unless otherwise indicated.
- c. Participants will be admitted to the CRU at least 12 hours prior to PF-07284890 dose on Day 1 of Period 1. Participants will be discharged on Day 4 of Study Period 3 following completion of all assessments.
- d. Medical history will include a history of prior illegal drug, alcohol, and tobacco use, as well as blood donation within prior 60 days. Medical history will be recorded at screening and updated on Day -1 of Period 1.
- e. Demographics will include participant race, ethnicity, age, and gender during the screening visit.
- f. Physical examination will be performed by trained medical personnel at the investigator site at screening or Day -1 of Period 1 only (height and weight must be obtained at screening to obtain BMI for eligibility criteria). A brief PE will be performed on Day -1 of Periods 2 and 3, and may be performed at other designated time points at the discretion of the investigator.
- g. Safety laboratory assessments including urinalysis, hematology, chemistry and coagulation will be performed at the indicated time-points, including Day -1 and Day 2 at 24 hours post-dose of all 3 Periods. All the safety laboratory samples must be collected following at least a 4-hour fast. Additional safety laboratory assessments may be performed at any time at the discretion of the investigator.
- h. For postmenopausal (amenorrheic for at least 12 consecutive months) female participants only.
- i. Urine drug and cotinine (mandatory) and alcohol breath test (at discretion of the investigator) will be performed at screening from Days -28 to -2 and again on Day -1 of Period 1. These tests may be performed at any other time at the discretion of the investigator.
- j. The investigator or his/her designee will discuss with the participant the need to use highly effective contraception consistently and correctly according to contraception guidelines.

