The total planned duration of participation, from the screening visit to the last Follow-up phone call, is up to approximately 11 weeks. Participants will be screened within 28 days prior to the first dose of investigational products and if all eligibility criteria are fulfilled, the participants will report to the CRU on Day -1 of Period 1 and will be required to stay in the CRU for 15 days and 14 nights.

Eligible participants will be admitted to the CRU at least 12 hours prior to the dosing of PF-07284890 on Day 1. On the morning of Day 1 of each period, participants will receive a single dose of 200 mg PF-07284890 as per randomization schedule. Study intervention will be administered with approximately 240 mL of ambient temperature water. In the fasted period (Sequence 1 Period 1 and Sequence 2 Period 2), participants will get their first dose after an overnight fast of at least 10 hours. In fed periods (Sequence 2 Period 1 and Sequence 1 Period 2 for the low-fat meal and Period 3 for the high-fat meal as shown in Section 1.2), following an overnight fast of at least 10 hours, participants should begin breakfast approximately 30 minutes prior to PF-07284890 administration. For Sequence 2 Period 1 and Sequence 1 Period 2, a low-fat (approximately 25% of total caloric content of the meal), low-calorie (approximately 400 to 500 calories) breakfast will be consumed over approximately a 20-minute interval with PF-07284890 administered within approximately 10 minutes of completion of the meal. For Period 3, a high-fat (approximately 50% of total caloric content of the meal), high-calorie (approximately 800 to 1000 calories) breakfast will be consumed over approximately a 20-minute interval with PF-07284890 administered within

approximately 10 minutes of completion of the meal. Serial PK samples will be collected up to 72 hours post dose for all periods. Period 2 will begin on Study Period 1, Day 5 (referred to as Period 2, Day -1). Period 3 will begin on Study Period 2, Day 5 (referred to as Period 3, Day -1). Participants will be discharged from the CRU at the end of Period 3, Study Day 4, following completion of all assessments.

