4.2. Scientific Rationale for Study Design

The objective of the study is to evaluate the effect of a low-fat or high-fat meal on the relative bioavailability of PF-07284890 following single 200-mg dose oral administration using a 100 mg tablet formulation of PF-07284890 in healthy adult participants. A crossover design is used to control variability between participants and account for any period effects. Between each administered single dose, a 5-day washout is proposed to minimize any residual PF-07284890 concentrations prior to start of the next period, which is sufficient based on the observed half-life of approximately 5.7 to 10 hours ([Table 4](#)).

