2.3. Study Design

This is a Phase 1, open-label, randomized, single dose, 3-treatment, 2-sequence, 3-period crossover study to evaluate the effect of a low-fat and high-fat meal on the relative bioavailability of PF-07284890 following a single oral dose of PF-07284890 using two 100-mg tablets of PF-07284890 in healthy adult participants, males and females of non-childbearing potential. The study will consist of 3 treatments: a single oral dose of 200 mg PF-07284890 (2 × 100 mg tablets) under fasted conditions (Treatment A, Reference), a single oral dose of 200 mg PF-07284890 (2 × 100 mg tablets) under low-fat meal fed conditions (Treatment B, Test 1), and a single oral dose of 200 mg PF-07284890 (2 × 100 mg tablets) under high-fat meal fed conditions (Treatment C, Test 2).

Approximately 12 healthy participants will be randomly assigned to study intervention such that approximately 6 participants will be enrolled to each sequence. Participants who discontinue from the study for non-safety reasons may be replaced at the sponsor's discretion in collaboration with the investigator.

Figure 1. C4471002 Study Schema

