3.5.1. Adverse Events

Any events occurring following start of treatment will be considered as treatment emergent adverse event (TEAE). Events that occur in a non-treatment period (ie washout or follow-up period) within the lag time of 28 days will be counted as treatment emergent and attributed to the previous treatment taken. Similarly, the time period for collecting AEs (“active collection period”) for each participant begins from the time the participant provides informed consent.

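### Laboratory abnormalities are counted by treatment without regard to the period baseline, so one that persists from an earlier period can be counted under a later treatment, with high-fat (always Period 3) most exposed

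*SAP*

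**What the plan says.** SAP 3.5.2 compares haematology, chemistry and urinalysis results with criteria held in the sponsor's reporting standards, and adds: "The assessment will not take into account whether each participant's baseline test result is within or outside the laboratory reference range". The same section sets a baseline for every period: "For each period, the baseline measurement is the predose measurement on Day -1". SAP 6.5.2 then has laboratory data listed and summarised by treatment, with the layout left to the sponsor's standards (CaPS).

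Footnote g to the Schedule of Activities (Protocol 1.3) places safety samples at several points, "including Day -1 and Day 2 at 24 hours post-dose of all 3 Periods". Protocol 4.1 fixes what Day -1 means after the first period: "Period 2 will begin on Study Period 1, Day 5 (referred to as Period 2, Day -1"; Period 3 follows Period 2 in the same way. It also fixes the fed periods: "Sequence 2 Period 1 and Sequence 1 Period 2 for the low-fat meal and Period 3 for the high-fat meal". The sequences are therefore fasted, low-fat, high-fat and low-fat, fasted, high-fat.

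Adverse events have an explicit attribution rule. Under SAP 3.5.1, an event arising in washout within 28 days "will be counted as treatment emergent and attributed to the previous treatment taken". The laboratory section has no matching rule.

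**The concern.** The Day -1 sample of Periods 2 and 3 is the one value that could show whether an abnormality was already there before the next dose. The SAP collects it, names it the baseline, and then sets baseline status aside when abnormalities are counted. A count under a given treatment can thus mix new findings with findings that began under the treatment before.

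In a crossover where each treatment appears equally often in each period, such carry-over would fall evenly. Here high-fat is always last, so it receives carry-over in all participants, while fasted and low-fat each receive it in half. Laboratory abnormalities are part of a stated secondary endpoint, and the high-fat meal is the condition expected to raise exposure most (Protocol 4.2.1). A small excess under high-fat would look plausible as a drug effect even if it came only from treatment order.

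The two safety tables can also disagree. A finding first seen on Day -1 and recorded as an adverse event goes to the previous treatment. If it is still present 24 h after the next dose, the laboratory count goes to the next treatment.

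**Working it through.** The plan gives no figure for this point, so there is none to reproduce. The check covers timing, expected counts and blood volume.

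**Timing.** Period 1 Day 5 is Period 2 Day -1 and the next dose follows a day later, so doses fall on study days 1, 6 and 11.
- Day -1 of Periods 2 and 3: (5 − 1) × 24 = about 96 h after the previous dose.
- Dose interval: 5 × 24 = 120 h. With half-lives of 5.7 to 10 h (Protocol 4.2), that is about 21 to 12 half-lives. Residual drug is at most 0.5^12 = 0.024%. Only a laboratory change that outlasts the drug can carry over.

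**Expected counts when the true incidence is the same under all three conditions.** From the documents: 12 participants, 6 per sequence (SAP 2.3), high-fat in Period 3. Assumed, because the documents give neither: p, the chance of a new abnormality per dose (0.05 to 0.20), and r, the chance that an abnormality at one 24-h sample is still present at the next period's 24-h sample (0 to 0.5).

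Flagged with baseline ignored: P1 = p; P2 = 1 − (1 − p)(1 − r·P1); P3 = 1 − (1 − p)(1 − r·P2). Fasted and low-fat each expect 6·P1 + 6·P2; high-fat expects 12·P3.

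For p = 0.10, r = 0.25:
- P2 = 1 − 0.9 × 0.975 = 0.1225
- P3 = 1 − 0.9 × 0.9694 = 0.1276
- Fasted and low-fat: 0.600 + 0.735 = 1.34 each
- High-fat: 12 × 0.1276 = 1.53, an excess of 0.20

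Of the carried counts, 12 × 0.0225 = 0.27 fall on fasted and low-fat together and 12 × 0.0276 = 0.33 on high-fat.

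Counting only abnormalities absent at the period's Day -1: N1 = p, and Nk = p(1 − r·P(k−1)) for Periods 2 and 3, taking whatever persists to the 24-h sample as visible at Day -1.

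| p | r | Fasted, low-fat (each) | High-fat | Excess | New only: fasted, low-fat (each) | New only: high-fat |
|---|---|---|---|---|---|---|
| any | 0 | 12p | 12p | 0 | 12p | 12p |
| 0.05 | 0.10 | 0.63 | 0.66 | 0.03 | 0.60 | 0.60 |
| 0.10 | 0.25 | 1.34 | 1.53 | 0.20 | 1.19 | 1.16 |
| 0.20 | 0.50 | 2.88 | 3.74 | 0.86 | 2.28 | 2.06 |

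Adding a 5% chance of a lasting pre-existing abnormality at p = 0.10, r = 0.25 raises all counts (1.87 and 2.05) but not the excess (0.19).

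**Blood sampling.** The Schedule of Activities lists 16 PK times per period, 13 of them up to 24 h, at about 3 mL each. Cumulative PK blood at the 24-h point:
- Period 1: 13 × 3 = 39 mL
- Period 2: 48 + 39 = 87 mL
- Period 3: 96 + 39 = 135 mL

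Fasted and low-fat each average (39 + 87)/2 = 63 mL, so the high-fat contrast is 135 − 63 = 72 mL. Assuming haemoglobin 14 g/dL, 5 L blood volume (range 4 to 6 L) and no regeneration, that is 72 × 14/5000 = 0.20 g/dL (0.17 to 0.25). Measured against the period's own Day -1, each period contains the same 39 mL, or 39 × 14/5000 = 0.11 g/dL.

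**The case against.** The other side has a good deal of substance.

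- A reader might infer that the Day -1 samples of Periods 2 and 3 serve only as the next baseline and are credited to no treatment. The SAP does not say so. It is silent on whether they also count as post-dose values, and the sponsor standards that govern the tables are not in the documents.
- A reader might infer that late abnormalities after fasted or low-fat dosing are lost. Protocol 8.3.5 requires clinically significant changes to be recorded as adverse events, SAP 3.5.1 assigns those to the previous treatment, and all laboratory data are listed. High-fat has no Day 5 sample either, since discharge is on Period 3 Day 4.
- A reader might infer that every carry-over runs to high-fat. Carry-over from Period 1 to Period 2 falls on fasted and low-fat in balance, and a lasting pre-existing abnormality is flagged under all three alike. Screening also excludes several abnormalities at entry.
- It is tempting to read the full 135 mL, 0.38 g/dL on the same assumptions, as an artefact of high-fat. The contrast is about 0.20 g/dL, the period baseline absorbs the earlier loss in change scores, and no criterion is shown to be crossed.
- The washout is long, "which is sufficient based on the observed half-life of approximately 5.7 to 10 hours", so drug carry-over is negligible and everything depends on persistence.
- The laboratory row of the schedule is broken in the available text and may carry a further mark after 24 h, so sampling on Day 4 cannot be ruled in or out.

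All of this limits the size and reach of the point. None of it removes the stated rule that baseline status is ignored, or the fixed position of high-fat.

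**Conclusion.** The point holds as a limited one. The SAP states that baseline status is ignored, and high-fat is Period 3 for everyone. An abnormality that persists across a dose can be counted under the later treatment, and the imbalance that remains falls on high-fat. With equal true incidence the expected excess is zero without persistence, about 0.2 of 12 participants at p = 0.10 and r = 0.25, and 0.03 to 0.86 across the positive-persistence scenarios tabulated. Those rates are assumptions. Cumulative sampling adds about 0.2 g/dL of haemoglobin difference on absolute values, under the assumptions above; it bears on the falls in red cell measures listed as a risk in Protocol 2.3.1.

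The consequence is confined to descriptive laboratory tables. No hypothesis is tested and the primary PK comparison is untouched. The documents do not support reading this as a loss of late abnormalities or as an error that always runs against high-fat.

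**What to change.** In SAP 3.5.2 and 6.5.2:

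1. Keep the planned table and listings. Add abnormality counts by treatment, split by normal or abnormal Day -1 baseline of that period, and identify as new only abnormalities that were absent or less severe at that baseline.
2. State that Day -1 values of Periods 2 and 3 are also shown as the preceding treatment's value at about 96 h, in line with SAP 3.5.1. Put them in a separate labelled row, not pooled with the 24-h comparison, because high-fat has no matching Day 5 sample and pooling would give fasted and low-fat an extra chance to be flagged.

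Under the assumptions above, item 1 removes the order-related excess and leaves at most a small deficit for high-fat (2.06 against 2.28 in the largest scenario), since fewer participants remain at risk of a new finding. It does not remove every period effect: a value brought close to a threshold by earlier sampling can still cross it for the first time in Period 3.

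The cost is SAP wording, one extra table split, one labelled row and small cell counts. All the data are already collected.

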3.5.3. Vital Signs

Supine blood pressure (BP), pulse rate (PR) and temperature will be measured at times specified in the SoA given in the protocol. Respiratory rate (RR) will be measured if the PR is outside of normal range.

For each period, the baseline measurement is the predose measurement on Day 1.

3.5.4. Electrocardiograms

QT interval, QTcF, PR, QRS and heart rate (HR) will be recorded at each assessment time indicated in the SoA given in the protocol. If not supplied, QTcF will be derived using Fridericia's heart rate correction formula:

$$\text{QTcF} = \text{QT} / (\text{RR})^{1/3} \text{ where RR} = 60/\text{HR} \text{ (if not provided)}$$

For each period, the baseline value is the average of the triplicate ECG measurements collected before dose administration on Day 1.

The maximum absolute value (postdose) and the maximum increase from baseline for QTcF, PR and QRS, over all measurements taken postdose, will be determined.

The maximum increase from baseline will be calculated by first subtracting the baseline value from each postdose measurement to give the change from baseline. The maximum of

these values over the respective period will then be selected, except in the case where a participant does not show an increase. In such an instance, the minimum decrease should be taken.

If more than 1 ECG is collected at a nominal time after dose administration (for example, triplicate ECGs), the mean of the replicate measurements will be used to represent a single observation at that time point. If any of the 3 individual ECG tracings has a QTcF value >500 ms, but the mean of the triplicates is not >500 ms, the data from the participant's individual tracing will be described in a safety section of the clinical study report (CSR) in order to place the >500 ms value in appropriate clinical context. However, values from individual tracings within triplicate measurements that are >500 ms will not be included in the categorical analysis unless the average from the triplicate measurements is also >500 ms. Changes from baseline will be defined as the change between the postdose ECG measurement and the predose baseline ECG value on Day 1.

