- k. All ECG assessments will be made after at least a 5-minute rest in a supine position and prior to any blood draws or vital sign measurements. Day 4 ECGs are for Period 3 only. Single ECGs are needed for screening, times after the study intervention has been administered, Day 4 of Period 3, and upon early termination/discontinuation, while triplicate ECGs are needed for baseline.

Visit Identifier Abbreviations used in this table may be found in Appendix 10	Screening^a	Periods 1-3^b												Follow-Up	Early Termination/Discontinuation				
		Days Relative to Day 1	Days -28 to -2	Day -1	Day 1								Day 2	Day 3	Day 4	28-35 days^t			
Hours After Dose			0	0.5	1	1.5	2	2.5	3	4	6	8	12	16	24	36	48	72	

- l. Single supine BP and PR will be performed following at least a 5-minute rest in a supine position. BP and PR assessments will be performed after collection of ECGs and prior to collection of blood draws if scheduled at the same time. Day 4 measurements are for Period 3 only. Temperature will be measured as per CRU standard practice. RR will be collected if the PR is outside of normal range.
- m. Full ophthalmic exam will be conducted if treatment emergent ocular AEs are observed.
- n. See Section [8.3.6](#) for details.
- o. PF-07284890 will be administered orally on Day 1 after overnight fasting until the start of study procedures for each treatment period. PF-07284890 will be administered orally and in fasted or fed state according to the conditions described in Protocol Section [5.3.2 Meals and Dietary Restrictions](#).
- p. One (approximately 3 mL) blood sample for PK analysis of PF-07284890 will be taken at the designated time points post dose in each treatment period.
- q. Retained Research Samples Prep D1 for Genetics: If not collected on the designated collection day, collect at the next available time point when biospecimens are being collected in conjunction with a participant visit. These samples will be collected during Period 1 only.
- r. Participants will be discharged on Day 4 of of Period 3 after completion of all assessment.
- s. Collect at pre-dose for all 3 periods. For fed periods (Sequence 2 Period 1 and Sequence 1 Period 2 for the low-fat meal and Period 3 for the high-fat meal), the ECGs should be done before the pre-dose PK sample, and both should be done before the meals.
- t. Contact may occur via telephone and must occur 28 to 35 days from administration of the final dose of study intervention.
- CC1

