6.5.4. Electrocardiograms

Changes from baseline for the ECG parameters HR, QTcF, PR interval, and QRS complex will be summarized by treatment and time postdose. The frequency of uncorrected QT values above 500 ms will be tabulated.

The number (%) of participants with maximum postdose QTcF values and maximum increases from baseline in the following categories will be tabulated by treatment:

Safety QTcF Assessment

Degree of Prolongation	Mild (ms)	Moderate (ms)	Severe (ms)
Absolute value	>450-480	>480-500	>500
Increase from baseline		30-60	>60

In addition, PR and QRS maximum values and maximum increases from baseline will also be tabulated by treatment using the following categories:

Safety PR and QRS Assessment

PR (ms)	Max. \geq300
PR (ms) increase from baseline	Baseline >200 and max. $\geq 25\%$ increase; Baseline ≤ 200 and max. $\geq 50\%$ increase
QRS (ms)	Max. \geq140
QRS (ms) increase from baseline	$\geq 50\%$ increase

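### The high-fat column of the maximum-ECG tables draws on one more scheduled reading (72 h) than the fasted and low-fat columns: a minor asymmetry that can only over-flag high-fat

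*SAP*

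**What the plan says.** SAP 3.5.4 defines the ECG maxima with no common time window: "The maximum absolute value (postdose) and the maximum increase from baseline for QTcF, PR and QRS, over all measurements taken postdose, will be determined". For the maximum increase, it subtracts the period's pre-dose triplicate mean from each post-dose value, and the maximum of "these values over the respective period will then be selected".

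SAP 6.5.4 compares treatments on these quantities: "The number (%) of participants with maximum postdose QTcF values and maximum increases from baseline in the following categories will be tabulated by treatment". It does the same for PR and QRS with their own categories. Protocol 9.3.2.1 has the matching QTcF table.

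On timing, footnote k of the Schedule of Activities (Protocol 1.3) says "Day 4 ECGs are for Period 3 only". Footnote s identifies the fed periods as "Sequence 2 Period 1 and Sequence 1 Period 2 for the low-fat meal and Period 3 for the high-fat meal", so every participant has the high-fat meal in Period 3, and the fasted and low-fat treatments occur only in Periods 1 and 2.

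Neither document sets the Day 4 ECG aside from the maxima or limits them to times shared by all periods. SAP 2.1 lists no modification to the protocol's analysis.

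**The concern.** If fasted and low-fat each have k scheduled post-dose ECGs, high-fat has k + 1. The largest of k + 1 noisy readings is on average higher than the largest of k, whatever the drug does. The additional reading also comes when little drug should remain, so it adds mostly noise.

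The 12-lead ECG is part of a secondary safety endpoint. Protocol 4.2.1 allows that the high-fat meal may raise exposure by up to about 2-fold, so the high-fat column is where a reader would look for an exposure-related QTcF effect. What is at stake is a false hint in that column. With 12 participants, one flagged person is about 8 percentage points (1/12).

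**Working it through.** **Drug left at 72 h.** The plan's own figure is in Protocol 5.3.5: discharge (Day 4 of Period 3) is more than 5 half-lives after the last dose. Protocol 4.2 gives an "observed half-life of approximately 5.7 to 10 hours".
- At 10 h: 72/10 = 7.2 half-lives; 2^(−7.2) = 0.68% remaining.
- At 5.7 h: 72/5.7 = 12.6 half-lives; 2^(−12.6) = 0.016% remaining.

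Both agree with the stated figure.

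**Inputs for the extra reading.**
- Number of common Day 1 post-dose ECGs, k: 3, as the Schedule of Activities row reads. The row is broken in the text available, so 2 to 5 is also shown.
- Baseline: mean of the pre-dose triplicate (SAP 3.5.4).
- Single-ECG within-participant SD, σ: assumed to be 8, 10 or 12 ms, because the documents give no ECG variability.
- Readings independent and normal, with no drug effect.

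**Expected maximum.** In SD units, the expected maximum of k independent normal readings is 0.56, 0.85, 1.03, 1.16 and 1.27 for k = 2, 3, 4, 5 and 6. Going from 3 to 4 adds 1.03 − 0.85 = 0.18 SD. With 2 common ECGs the gain is 0.28 SD, and with 5 it is 0.10 SD. The extra reading is the maximum with probability 1/(k + 1): 25% for k = 3, and 33% to 17% for k = 2 to 5.

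**Chance of an increase of at least 30 ms.** With baseline error b ~ N(0, σ²/3), the chance is 1 − E[Φ((30 + b)/σ)^k]. For k = 3 against k = 4:

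| Assumed SD | Shift in expected maximum | Per participant | Expected number of 12 | At least 1 of 12 |
|---|---|---|---|---|
| 8 ms | 1.5 ms | 0.17% to 0.23% | 0.02 to 0.03 | 2.1% to 2.7% |
| 10 ms | 1.8 ms | 1.4% to 1.8% | 0.16 to 0.22 | 15% to 20% |
| 12 ms | 2.2 ms | 4.3% to 5.6% | 0.52 to 0.67 | 41% to 50% |

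The last two columns are 12p and 1 − (1 − p)^12, using unrounded p. The per-participant ratio is about 1.3 throughout. For an increase above 60 ms, the chance stays below 0.004% with or without the extra reading.

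**If the drug does raise Day 1 QTcF** (k = 3, SD 10, same effect at each Day 1 time and none at 72 h):

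| Day 1 drug effect | Shift in expected maximum | Ratio of chances, at least 30 ms |
|---|---|---|
| 0 ms | 1.8 ms | 1.32 |
| 5 ms | 0.9 ms | 1.09 |
| 10 ms | 0.4 ms | 1.03 |

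**With the Day 4 ECG left out**, all three treatments have k scheduled readings. At k = 3 the no-effect expected maximum is 0.85 SD in each, and the built-in gap is zero.

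**The case against.** The case for leaving the rule alone is substantial.

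- **The absolute size is very small.** A 1.3-fold ratio sounds larger than it is: in 12 people it is between about 0.01 and 0.16 of one extra flagged participant. This stands, and it is why the point is optional.
- **The error is in the cautious direction.** An added reading can raise the high-fat maximum but never lower it, and the effect fades when the drug itself moves Day 1 QTcF. This stands.
- **No inference depends on the table.** No hypothesis is tested and safety is summarised descriptively. The participant-level ECG rules in Protocol 7.1.1 and 8.3.3 act on a participant's own readings, not on this table. This stands.
- **The 72 h values are visible elsewhere.** SAP 6.5.4 also summarises change from baseline by treatment and time. This stands in part: the categorical tables still absorb the 72 h value without marking it.
- **Taking the worst post-dose value is a normal safety convention.** It is, but the convention does not require unequal scheduled readings in columns set side by side.

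A reader might go further than the documents allow in four ways:

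- That high-fat always has more ECGs. This holds for scheduled readings only; early-termination, unscheduled and triggered repeat ECGs can arise under any treatment.
- That the PR and QRS categories are inflated too. The same rule applies to them, but no effect has been shown on those categories, nor on the absolute QTcF bands.
- That the 72 h reading is certainly drug-free. The half-lives come from patients dosed fasted, and the fed half-life is something this study will estimate. The unequal count remains either way.
- That every reading outside the shared schedule should leave the maxima. Removing unscheduled or triggered repeats could hide a real prolongation.

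**Conclusion.** The asymmetry is real but minor. By the plan's own schedule and definitions, the high-fat maxima rest on one more scheduled ECG than the fasted and low-fat maxima. The direction holds for any number of common Day 1 ECGs. The size for QTcF rests on three common readings, independent normal errors, no drug effect and the assumed SDs: about 0.18 SD on the expected maximum, and about a 1.3-fold chance of reaching 30 ms, starting from low probabilities. The only harm is a slightly greater chance of a false high-fat signal. The documents do not support reading this as a material bias in the safety conclusions or as a way to miss a high-fat prolongation. Severity: optional.

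**What to change.** In SAP 3.5.4 and 6.5.4, state that the by-treatment maxima and categories exclude the scheduled Period 3 Day 4 ECG. Keep unscheduled and triggered repeat post-dose ECGs in the maxima for every treatment. Add one table line for the maximum at any time including Day 4, and a listing, so that no value above a threshold is lost.

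The cost is one SAP sentence, a programming filter and one extra table line. The ECG schedule does not change and no data are discarded. The fix equalises scheduled readings only: high-fat is always given in Period 3, so its ECG results remain confounded with period, and a table footnote could say so.
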